#### **Protocol Template**

Sponsor: Menarini Pharmaceutical Study Code: MEIN/19/ZoNe-HYP/001

Protocol Version 1 of 16/07/2020

the site, the PI, the local laboratory, the CRO receive a request for data privacy rights exercise, the concerned recipient shall immediately inform the Sponsor DPO by e-mail at [contact]. The request shall be fulfilled within the term set forth by the applicable privacy laws (normally 30 days). The Sponsor, the site, the PI, the local laboratory, the CRO shall implement adequate organizational measures to reply to patients within the above-mentioned deadline.

#### 19.9 Future research

With patients' optional and additional consent, the Sponsor and/or the site may use the data collected during the course of the study for further medical and scientific research purposes. These may include, eg, retrospective clinical studies; clinical studies pertaining to the patients' pathology/medical condition(s)or similar conditions; studies which compare the data of this study with those from other sources to identify the factors involved in a disease; registration of new drugs

In the context of these additional research activities, patients' data will be processed, pseudonymized and transferred abroad and may be shared with future research partners.

In the context of these additional research activities, patients' data will be processed, anonymized and transferred abroad, and may be shared with future research partners –in most cases this will prevent patient's identification; however, in the unlikely event patients full identity really needs to be disclosed, the same precautions and safeguards as those described in this protocol will be implemented.

## 20. DATA HANDLING AND RECORDS KEEPING

Unless other laws require archiving for a longer period, the site and the PI shall archive the content of the clinical trial file, including the relevant patients' personal data, for at least 25 years after the end of the clinical trial. However, medical records shall be archived in accordance with the national laws of the country where the study is performed.

The Investigator should keep all study related documents, as specified in ICH E6 (GCP) Section 8 and by the applicable regulatory requirement(s), in the Investigator's File.

Identification Number: FORM-000050125

Previous Doc Number:
CTWI10A

Version Number: 1.0, CURRENT

#### **Protocol Template**

Sponsor: Menarini Pharmaceutical Study Code: MEIN/19/ZoNe-HYP/001

Protocol Version\_1 of 16/07/2020

The media used to archive the content of the clinical trial file shall be such that the content remains complete and legible throughout the period referred to in the first paragraph. Any modification to the content of the clinical TMF shall be traceable

The content of the Investigator's File shall be archived in a way that ensures that it is readily available and accessible, upon request, to the competent authorities.

If the responsible Investigator retires, relocates, or for other reasons withdraws from the responsibility of keeping the study records, custody must be transferred to a person who will accept the responsibility.

The Sponsor must be notified in writing of the name and address of the new custodian.

#### 21. PUBLICATION POLICY AND RESULTS

By signing the study protocol, the Investigator (and his/her appointed staff) ensures that any information and all the study documents provided by the Sponsor will be maintained strictly confidential.

None of this material may be disclosed to any party not directly involved in the study without written permission from Sponsor.

All information concerning the study, the drug as well as data and results of the study are confidential and property of the Sponsor.

The Sponsor will prepare the final report, including the statistical and clinical evaluations, and trial results will be posted and made public, according to applicable Regulatory Regulations. The Investigator's agreement and signature will be obtained, and a copy will be provided to the Investigator.

Sponsor reserves the exclusive right to publish and present data and results of the present study at scientific meetings, or to submit these clinical trial data to national and international regulatory authorities. The Investigator may not use the results of this study for publication or presentation without written authorization from Sponsor.

Identification Number: FORM-000050125

Previous Doc Number: CTWI10A

Version Number: 1.0, CURRENT

Sponsor: Menarini International Operations Luxembourg Study Code: MEIN/19/ZoNe-HYP/001

Protocol Version\_1 of 16/07/2020

otaay coaci mem, io/ecito iiii /oo.

**Protocol Template** 

Sponsor: Menarini Pharmaceutical Study Code: MEIN/19/ZoNe-HYP/001

Protocol Version\_1 of 16/07/2020

## 25. APPENDICES

25.1 Appendix 1: Declaration of Helsinki

### **MODIFICATION HISTORY**

Unique			
Identifier	Date of the		
for this	Document		Significant Changes from
Version	Version	Author	Previous Authorized Version
V1.0	14Dec2021	[name]	Not Applicable. First version

Document: \\ieedc-vnasc01\BIOSdata\Menarini\NebZof\KZA41200\Biostatistics\Documentation\SAP

Author: [name] Version Number: Final V1.0

Version Date: [14Dec2021]

Template No.: CS\_TP\_BS016 Revision 6 Reference: CS\_WI\_BS005

Page 5 of 37

#### LIST OF ABBREVIATIONS AND DEFINITION OF TERMS

ACE-i angiotensin converting enzyme-inhibitors

ACS Abnormal, Clinically Significant

ADaM analysis data model ADR adverse drug reaction

AE adverse Event

AEOSI adverse event of special interest ANCS abnormal, not clinically significant ATC anatomical therapeutic chemical

BB beta blocker
BP blood pressure
BMI body mass index

CTMS clinical trials management system

DBL data base lock DBP diastolic BP

DMC data monitoring committee

ECG electrocardiogram

eCRF electronic case report form

EOT end of treatment

ENR enrolled ITT Intent-to-treat

MCMC markov chain monte carlo

MedDRA medical dictionary for regulatory activities

MI multiple imputation

NEB Nebivolol

PD protocol deviation PP per protocol PT preferred term

SAE serious adverse event

SAF safety

SAP statistical analysis plan

SBP systolic BP

SD standard deviation

SDTM study data tabulation model

SOC system organ class

TEAE treatment emergent adverse events

WHO world health organization ZOF zofenopril calcium

Document: \\ieedc-vnasc01\BIOSdata\Menarini\NebZof\KZA41200\Biostatistics\Documentation\SAP

Author: [name] Version Number: Final V1.0

Version Date: [14Dec2021]

Template No.: CS\_TP\_BS016 Revision 6 Reference: CS\_WI\_BS005

Page 6 of 37

Document: \\ieedc-vnasc01\BIOSdata\Menarini\NebZof\KZA41200\Biostatistics\Documentation\SAP

Author: [name] Version Number: Final V1.0

Version Date: [14Dec2021]

Template No.: CS\_TP\_BS016 Revision 6 Reference: CS\_WI\_BS005

Effective Date: 02Dec2019

#### Page 7 of 37

#### 1. Introduction

This document describes the rules and conventions to be used in the presentation and analysis of efficacy and safety data for Protocol MEIN/19/ZoNe-HYP/001. It describes the data to be summarized and analyzed, including specifics of the statistical analyses to be performed.

This statistical analysis plan (SAP) is based on protocol version 1.0 dated 16JUL2020 and addendum version 1.0 dated 29OCT2020.

### 2. STUDY OBJECTIVES AND ESTIMANDS

### 2.1. PRIMARY OBJECTIVE

To assess the antihypertensive effect of the extemporaneous combination of zofenopril calcium(ZOF) 30 mg or nebivolol(NEB) 5 mg in lowering sitting diastolic blood pressure(DBP) after 8 weeks of treatment, in patients with uncontrolled blood pressure(BP) who were previously treated with NEB or ZOF monotherapies for at least 4 weeks

#### 2.2. SECONDARY OBJECTIVES

The secondary objectives are,

- To assess the antihypertensive effect of the extemporaneous combination of NEB 5 mg and ZOF 30 mg in lowering sitting systolic blood pressure (SBP) after 8 weeks of treatment in patients with uncontrolled BP, after at least 4 weeks of treatment with NEB or ZOF monotherapies
- To evaluate the total number and percentage of patients who achieved the BP goal (sitting BP ≤130/80 mmHg) at Visit 2 and Visit 3
- To assess compliance to the monotherapy and extemporaneous combination (actual doses taken versus planned doses to be taken)
- To evaluate the safety and tolerability of the ZOF and NEB monotherapies, and the extemporaneous combination of NEB 5 mg and ZOF 30 mg after 8 weeks of treatment

#### 2.3. EXPLORATORY OBJECTIVES

The exploratory objectives are,

Document: \\ieedc-vnasc01\BIOSdata\Menarini\NebZof\KZA41200\Biostatistics\Documentation\SAP

Author: [name] Version Number: Final V1.0

Version Date: [14Dec2021]

Template No.: CS\_TP\_BS016 Revision 6 Reference: CS\_WI\_BS005

Page 12 of 37

- To assess the antihypertensive efficacy at different time points in patients who
  - 1. received NEB or ZOF monotherapies before the run-in period,
  - 2. received any other ACE-i or BB monotherapies before the run-in period
- To assess the antihypertensive effect on patients, based on their hypertension grade, presence or absence of hypercholesterolemia, presence or absence of diabetes at Visit 2 and Visit 3

### 2.4. ESTIMANDS

Estimand	Definition	Attributes			
		Population	Variable/Endpoint	Intercurrent event handling strategy	Population- level summary measure
Primary Estimand		Intent-To- Treat (ITT)	Change in mean sitting DBP between Week 0 (Visit 2) and Week 8	The patients will not be permitted to use any of the Blood pressure modifying medications from Screening till the end of treatment.	Difference in mean DBP with P-value
Secondary Estimand 1		Intent-To- Treat (ITT)	Change in mean sitting SBP between Week 0 (Visit 2) and Week 8	The patients will not be permitted to use any of the Blood pressure modifying medications from Screening till the end of treatment.	Difference in mean SBP with P- value
Secondary Estimand 2		Intent-To- Treat (ITT)	The number of patients achieving BP goal (sitting BP ≤130/80 mmHg)	The patients will not be permitted to use any of the Blood pressure modifying medications from Screening till the end of treatment.	Difference in proportion of patients achieving BP goal between Week 0 (Visit 2) and Week 8 with P-value

Document: \\ieedc-vnasc01\BIOSdata\Menarini\NebZof\KZA41200\Biostatistics\Documentation\SAP

Author: [name] Version Number: Final V1.0

Version Date: [14Dec2021]

Template No.: CS\_TP\_BS016 Revision 6 Reference: CS\_WI\_BS005

Page 13 of 37

#### 3. STUDY DESIGN

#### 3.1. GENERAL DESCRIPTION

This is a phase IV, open-label, multicenter, multinational study with 2 study periods (a run-in period of 4 weeks and an assessment period of 8 weeks). Grade 1-2 hypertensive patients (blood pressure [BP] ranging from  $\geq$ 140/90 mmHg to  $\leq$ 179/109 mmHg) on treatment with any angiotensin converting enzyme-inhibitors (ACE-i) or beta blockers (BBs) including ZOF 30 mg or NEB 5 mg respectively will be screened for eligibility (Visit 1). On the same day, the eligible patients will enter into a run-in period after Screening, during which:

- Patients on ZOF 30 mg or NEB 5 mg will continue the same therapy for 4 weeks
- Patients on any other ACE-i will be assigned to monotherapy with ZOF 30 mg while patients on any other BB will be assigned to monotherapy with NEB 5 mg, respectively, for 4 weeks.

After the 4 weeks of monotherapy in the run-in period, if BP at Visit 2, remains uncontrolled (sitting SBP/DBP >130/80 mmHg) despite an adherence to the treatments ranging from 80% to 120%, the patients will start treatment (Week 0, Visit 2) with the extemporaneous combination of NEB 5 mg/ZOF 30 mg (NEB/ZOF) and will be assessed for further 8 weeks (assessment period). If the patients, at Visit 2 after the Run-In period, have controlled BP (sitting SBP/DBP ≤130/80 mmHg), and/or do not tolerate the treatment, and/or do not maintain the adherence to the therapy (range from 80% to 120%), these patients will not be continued further in the study. At the end of the assessment period (Visit 3) the antihypertensive effect of the extemporaneous combination of NEB 5 mg and ZOF 30 mg will be evaluated. A total number of 290 patients will be screened considering 25% of drop-out rate, to obtain approximately 216 completed patients at the end of the study.

Document: \\ieedc-vnasc01\BIOSdata\Menarini\NebZof\KZA41200\Biostatistics\Documentation\SAP

[figure not shown]
Author: [name] Version Number: Final V1.0

Version Date: [14Dec2021]

Template No.: CS\_TP\_BS016 Revision 6 Reference: CS\_WI\_BS005

Page 14 of 37

Figure 1: Study Scheme

BP: Blood pressure, NEB: Nebivolol, ZOF: Zofenopril calcium, ACE-i: Angiotensin converting enzyme-inhibitors, BB: Beta blockers

### 3.2. SCHEDULE OF EVENTS

Study Procedures/ Assessments	Visit 1 (Week -4)	Visit 2 (Week 0) a	Visit 3 (Week 8)
	Screening + Start of Run-in Period b	Start of Assessment Period	End of Assessment Period
Informed consent	X		
Inclusion/exclusion criteria	X		
Medical history	X		
Prior medication	X		
Demography (age, sex, race)	X		
Concurrent diseases and medical conditions	X	X	X
Antihypertensive treatment with NEB or ZOF monotherapy c	X		
Study drug dispensing d		X	
Study drug return and accountability (Compliance assessment)		Xe	X f

Document: \\ieedc-vnasc01\BIOSdata\Menarini\NebZof\KZA41200\Biostatistics\Documentation\SAP

Author: [name] Version Number: Final V1.0

Version Date: [14Dec2021]

Template No.: CS\_TP\_BS016 Revision 6 Reference: CS\_WI\_BS005

Effective Date: 02Dec2019

Page 15 of 37

Concomitant medications	X	X	X
Urine pregnancy test	X	X	X
Physical examination	X	X	X
Vital signs	X	X	X
Laboratory test g	X		X
Blood pressure	X	X	X
ECG	X	X	X
AE/SAE assessment	X	X	X h

ACE-i: Angiotensin converting enzyme-inhibitors; AE: Adverse event; BB: Beta blockers; ECG: electrocardiogram; EOT: End of treatment; NEB: nebivolol; SAE: serious adverse event; ZOF: zofenopril calcium

- a: For Visit 2, a window of ±2 days will be allowed at Week 0; and for Visit 3, a window of ±3 days will be allowed at Week 8
- b: Patients meeting the eligibility criteria at Screening, will enter the run-in period on the same day
- c: Patients on ZOF 30 mg or NEB 5 mg at Screening will continue the same therapy. Patients on any other
- ACE-i or BBs at Screening will be assigned to monotherapy with ZOF 30 mg or NEB 5 mg, respectively
- d: Patients will be provided with the extemporaneous combination of NEB 5 mg with ZOF 30 mg
- e: Adherence to monotherapies will be checked at the beginning of Visit 2
- f: Adherence to the extemporaneous combination of NEB 5 mg with ZOF 30 mg will be checked at the end of Visit 3
- g: To ensure patient safety, the patients will be contacted over phone within 24 hours, in case of any abnormality and clinically relevant laboratory test according to the Investigator's judgement at any visit h: Patients having any ongoing AE/SAE at the end of the treatment, will be followed for further 2 weeks via a phone call to check about the status of the AE/SAE

#### CHANGES TO ANALYSIS FROM PROTOCOL 3.3.

As per protocol, the definition of Per Protocol Population is "All patients included in the safety population who do not have any major protocol deviations will be included in this population". In SAP, this has been updated to,

\\ieedc-vnasc01\BIOSdata\Menarini\NebZof\KZA41200\Biostatistics\Documentation\SAP Document:

Final V1.0 Author: **[name]** Version Number:

> Version Date: [14Dec2021]

Template No.: CS TP BS016 Revision 6 Reference: CS\_WI\_BS005

Page 16 of 37

"The per-protocol (PP) population will contain all patients in the SAF population who have not experienced major protocol violations that could affect the efficacy analyses".

The primary endpoint analysis includes only 2 two consecutive visits, i.e. Baseline (week 0) and one post baseline (Week 8). The protocol suggested multiple imputation (MI) simulation method for imputing missing data is not applicable in this scenario. MI method may not be appropriate for a longitudinal study with only two time-points data. Thus, it has been agreed not to perform multiple imputation, and the primary analysis will be performed only on the observed data.

- The secondary and exploratory analysis use McNemar's test to analyze proportion of patients achieving BP goal (SBP/DBP <=130/80 mmHg) between visit 2 and visit 3. As per the entry criteria to the combination therapy, only those patients with uncontrolled BP (SBP/DBP > 130/80 mmHg) at visit 2 are eligible. So, the proportion of patients achieving the BP goal at visit 2 will be always zero. Thus, SAP has been updated with exact McNemar's test instead of McNemar's test.
- The products involved in this study are well established in the market for many years with an excellent safety profile. The term AEOSI is mentioned in the study protocol by error and no adverse events of special interest (AEOSI) have been identified which require special monitoring during the study. Thus, no analysis is performed on AEOSIs in the study.

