## 14.4 Analysis Variables

Analysis of Variables and Populations Used				
Efficacy				
	Analysis Variables	Population Used		
Primary efficacy	Change in mean sitting DBP between Week 0 (Visit 2) and Week 8	ITT population,		
1 Illiary Cilicacy	(Visit 3)	PP population		
Secondary efficacy	Change in mean sitting SBP between Week 0 (Visit 2) and Week 8	ITT population,		
Secondary efficacy	(Visit 3)	PP Population		
	Number and proportion of patients achieving the BP goal (sitting BP ITT pop			
	≤130/80 mmHg) at Week 0 (Visit 2) and Week 8 (Visit 3)			
	Adherence to treatment will be measured through treatment	Enrolled population,		
	compliance which is 100 × (actual doses taken/ planned doses)  Safety popul			
Exploratory efficacy	Change in mean sitting SBP and DBP between Visit 1 and Visit			
	2 in the group of patients on ZOF 30 and NEB 5 mg and in the			
	group of patients switched to ZOF 30 mg or NEB 5 mg from			
	any other ACE-I and BB			
	Change in mean sitting SBP and DBP between Visit 1 and Visit	Enrolled Population		
	3 in the group of patients on ZOF 30 mg and NEB 5 mg or in			
	the group of patients switched to ZOF 30 mg or NEB 5 mg from			
	any other ACE-i and BB			
	Number and proportion of patients in the group of patients on			

Identification Number: FORM-000050125

Previous Doc Number: CTWI10A

Version Number: 1.0, CURRENT

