# **5.2.** Intent-to-treat [ITT] Population

The intent-to-treat (ITT) population will contain all patients in the ENR population and receive at least 1 dose of study drug (combination therapy) and have at least 1 post baseline safety assessment

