# 5.3. SAFETY [SAF] POPULATION

The safety (SAF) population will contain all patients who are in the ENR population and receive at least 1 dose of study drug (combination therapy)

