#### 16.2.2. ANALYSIS OF SECONDARY EFFICACY VARIABLES

Secondary efficacy variables will be summarized in a descriptive manner using ITT population.

• Change in mean sitting SBP between Week 0 (Visit 2) and Week 8 (Visit 3):

Change from baseline in sitting SBP from prior and post combination therapy will be compared using paired t-test. The p-value will be presented using a paired t-test comparing mean at baseline and mean at Week 8. The secondary endpoint will be presented in a descriptive manner using n, mean, median, SD, Q1, Q3, and minimum and maximum.

Assumption of normality will be investigated using Wilk-Shapiro test. If violation is observed, then paired t-test will be replaced by Wilcoxon signed rank test.

• The number of patients achieving BP goal (sitting BP ≤130/80 mmHg) will be summarized for Visit 2 and Visit 3, along with percentage. A p-value using exact McNemar's test will be presented to compare the proportion of patients achieving the BP goal (sitting BP ≤130/80 mmHg) between Visit 2 and Visit 3.

Document: \\ieedc-vnasc01\BIOSdata\Menarini\NebZof\KZA41200\Biostatistics\Documentation\SAP

Author: [name] Version Number: Final V1.0

Version Date: [14Dec2021]

Template No.: CS\_TP\_BS016 Revision 6 Reference: CS\_WI\_BS005

Page 27 of 37

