#### 16.3.2. ANALYSIS OF EXPLORATORY EFFICACY VARIABLES

Exploratory efficacy variables will be summarized in a descriptive manner using safety population for Visits 1, 2 and 3.

- Change in mean sitting SBP and sitting DBP between Visit 1 and Visit 3 will be analyzed as following:
- Change from baseline in sitting SBP and DBP from prior (Visit 1) and post (Visit 3) combination therapy will be compared using paired t-test. The p-value will be presented using a paired t-test comparing mean at baseline and mean at Week 8. The exploratory endpoint will be presented in a descriptive manner using n, mean, median, SD, Q1, Q3, and minimum and maximum. Assumption of normality will be investigated using Wilk-Shapiro test. If violation is observed, then paired t-test will be replaced by Wilcoxon signed rank test.
- The number of patients achieving BP goal (sitting BP ≤130/80 mmHg) will be summarized for Visit 2 and Visit 3, along with percentage. A p-value using exact McNemar's test will be presented to compare the proportion of patients achieving the BP goal (sitting BP ≤130/80 mmHg) between Visit 2 and Visit 3.
- The number of patients achieving BP goal (sitting BP ≤130/80 mmHg) will be summarized for Visit 2 and Visit 3, along with percentage for each of the subgroup specified under section 7.5 of the SAP.

Document: \\ieedc-vnasc01\BIOSdata\Menarini\NebZof\KZA41200\Biostatistics\Documentation\SAP

Author: [name] Version Number: Final V1.0

Version Date: [14Dec2021]

Template No.: CS TP BS016 Revision 6 Reference: CS WI BS005

Page 28 of 37

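### The Visit 2 goal rate is 0% by construction, exact McNemar cannot go against the combination, and the SAP text plans no table of run-in adverse events

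*SAP*

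**What the plan says.** SAP 5.2 limits ITT to Enrolled patients who "receive at least 1 dose of study drug (combination therapy) and have at least 1 post baseline safety assessment". SAP 5.3 also requires a combination dose for the Safety population, and the per-protocol set (5.4) is a subset of Safety. Under SAP 3.1, patients leave at Visit 2 if they have controlled BP "and/or do not tolerate the treatment, and/or do not maintain the adherence to the therapy".

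On the goal rate, SAP 16.2.2 uses ITT, and an exact McNemar p-value "will be presented to compare the proportion of patients achieving the BP goal (sitting BP ≤130/80 mmHg) between Visit 2 and Visit 3". Secondary Estimand 2 (SAP 2.4) has the matching summary measure: "Difference in proportion of patients achieving BP goal between Week 0 (Visit 2) and Week 8 with P-value". SAP 3.3 admits the difficulty, "So, the proportion of patients achieving the BP goal at visit 2 will be always zero", and responds only by changing McNemar to exact McNemar.

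On the run-in BP results, SAP 16.3.2 states: "Exploratory efficacy variables will be summarized in a descriptive manner using safety population for Visits 1, 2 and 3". Protocol 14.5.5 says the same, but the table in protocol 14.4 names the Enrolled population for exploratory efficacy.

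On safety, SAP 2.2 includes the safety and tolerability of the two monotherapies among the secondary objectives. SAP 18 puts all safety outputs on the Safety population. SAP 18.1 starts the treatment-emergent clock at the first combination dose, and every adverse event summary in 18.1.1 to 18.1.4 is of treatment-emergent events, apart from SAP 18.1.3 and 18.1.4 also defining the events by their eCRF category. Other events go to listings.

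**The concern.** Every set used for these outputs is selected on the outcome of the run-in. Patients who reached goal on monotherapy, could not tolerate it or did not adhere to it are removed before the run-in is described.

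Three outputs suffer. First, the secondary objective on the number at goal at Visit 2 is answered with 0% whatever the monotherapies achieved, and that zero is then the comparator in a significance test. Second, the exploratory Visit 1 to Visit 2 BP changes describe only patients who did not reach goal on monotherapy. Third, the patients who say most about monotherapy tolerability, those who stopped because of it, appear in no adverse event table described. The trial is presented as the combination versus each monotherapy, so a reader may take 0% as the monotherapy result and the p-value as evidence of superiority.

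**Working it through.** **Inputs.** Completers 216 and screened 290 (protocol 14.2, SAP 3.1); two-sided 5% tests (SAP 6.5); entry and goal thresholds of 130/80 mmHg (SAP 3.1, 16.2.2). The documents give no expected goal rate at either visit.

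**1. The SAP's zero reproduces.** Taking goal as both components at or below threshold, no combination of SBP and DBP satisfies both the entry rule and the goal. This is so whether entry means either component above or both above. It fails only if entry means either above and goal means either at or below. A controlled patient dosed in error could also make the rate non-zero.

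**2. The test.** McNemar compares patients moving into goal (k) with patients moving out of it (here 0). The exact two-sided p-value is then 2 × 0.5^k:
- k = 5: 2 × 0.03125 = 0.0625
- k = 6: 2 × 0.015625 = 0.031, with 6/216 = 2.8% at goal at Visit 3

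Asymptotic McNemar without continuity correction would reject from k = 4 (p = 0.0455). The change to the exact version therefore moves the threshold from 4 to 6 responders and leaves the structure alone. The null of equal discordant cells amounts to a Visit 3 goal rate of zero.

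**3. Chance of p < 0.05.** This is P(X ≥ 6) for X ~ Binomial(216, q), with q an assumed Visit 3 goal rate:

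| q | P(p < 0.05) |
|---|---|
| 1% | 0.02 |
| 2% | 0.27 |
| 3% | 0.63 |
| 5% | 0.96 |
| 10% | >0.99 |

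Some responders would appear without any drug effect. One simulation assumed true SBP mean 140 to 145 (SD 10), true DBP mean 88 (SD 7), and visit-to-visit SD of 6 to 8 systolic and 3.6 to 4.8 diastolic. Fluctuation alone then put 1.1% to 2.8% at goal at Visit 3, giving p < 0.05 in about 3% to 56% of trials. None of these inputs is in the documents.

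**4. What the zero may hide.** The planned loss is 290 − 216 = 74 (25.5%), not split by cause. Suppose m patients are controlled at Visit 2 beside 216 uncontrolled entrants. The Visit 2 goal rate is m/(216 + m):

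| m | Visit 2 goal rate | ITT table shows |
|---|---|---|
| 0 | 0% | 0% |
| 15 | 15/231 = 6.5% | 0% |
| 29 | 29/245 = 11.8% | 0% |
| 44 | 44/260 = 16.9% | 0% |
| 74 | 74/290 = 25.5% | 0% |

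**5. Run-in BP.** Protocol 14.5.5 and SAP 16.3.2 use Safety; the protocol 14.4 table names Enrolled. In the text available the Enrolled label sits beside the Visit 1 to Visit 3 row, and it is read here as covering the whole exploratory block. SAP 3.3 does not mention the conflict.

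**6. Run-in adverse events.** Protocol 10.2 counts events after the first dose of study treatments, and protocol section 9 includes run-in NEB or ZOF among the treatments. The SAP clock starts four weeks later, and SAP 3.3 does not declare this. An event confined to the run-in, with known dates, is not treatment-emergent and reaches a listing at most. If the Safety-population rule of SAP 18 also governs listings, events in patients who never took the combination may not appear even there.

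**The case against.** The SAP discloses the zero. The Visit 3 count and percentage in ITT are already planned, and SAP 9.1 presents withdrawals and reasons for exclusion on Enrolled, so an approximate count of monotherapy responders may be recoverable. The test is not automatically significant: five responders or fewer do not reach 5%, and if one patient dosed in error moved out of goal, eight would be needed. All this stands, but it concerns how often the test rejects and what can be pieced together. Disposition is not a Visit 2 goal rate, and the test still has only one possible direction.

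The range in step 4 is open to challenge. It leaves out intolerant, non-adherent and later-lost patients who may have a Visit 2 reading. With 290 as denominator, 15, 29 and 44 controlled patients give 5.2%, 10.0% and 15.2%. The top value needs every planned loss to be a controlled patient, although protocol 14.2 counts screen failures in the 25%. The range is illustrative; the planned table shows 0% throughout it.

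On run-in BP, the protocol text and the SAP agree on Safety, and the reading of the 14.4 table cannot be confirmed from the extracted text. The selection problem does not depend on that reading.

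On safety, protocol 14.5.7 promises a presentation of all adverse events, SAP 18.5 summarises vital signs for monotherapy, SAP 18.2 tabulates deaths during the study, and Appendix 1 defines monotherapy columns. Table detail is left to templates that were not available, nor was the protocol addendum. The point is therefore limited to the SAP text. There, the vital-sign and death summaries still fall under the Safety-population rule, and no run-in adverse event table is described.

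**Conclusion.** The concern holds and should be fixed. For patients who met the entry rule, the Visit 2 goal rate in ITT is zero by construction, and exact McNemar becomes a count of Visit 3 responders that reaches p < 0.05 at 6 of 216. The objective on goal attainment at Visit 2 and the adverse event part of the objective on monotherapy safety are not answered as planned. The exploratory run-in BP results describe a group selected for non-response.

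The p-value thresholds follow from arithmetic, assuming 216 analysed patients and no entry deviations. The rejection probabilities and the possible Visit 2 rates rest on assumed values. The primary endpoint is unaffected, as are monotherapy exposure, compliance and disposition, which are on Enrolled.

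**What to change.** 1. In SAP 16.2.2, drop the McNemar p-value and report the Visit 3 goal rate in ITT with an exact (Clopper-Pearson) 95% CI. For illustration, 65/216 = 30.1% has the interval 24.1% to 36.7%. Change the Secondary Estimand 2 summary measure to match. Report the Visit 2 goal rate separately, in all Enrolled patients with a Visit 2 reading. McNemar on Enrolled is no substitute, because controlled patients leave at Visit 2 and have no planned Visit 3 value on the combination.
2. Resolve protocol 14.4 against 14.5.5 in SAP 3.3. Use Enrolled for Visit 1 to Visit 2 BP changes and Visit 2 goal rates, by run-in drug and by continued versus switched.
3. Define a run-in safety set: Enrolled patients with at least one run-in dose of ZOF or NEB. Tabulate run-in adverse events, serious events and events leading to non-continuation by drug, apart from the combination-period tables.

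The cost is SAP wording, a few tables from data already collected and one secondary p-value. The primary analysis does not change, and protocol 14.7 provides for SAP revisions of this kind to be finalised before database lock.
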